- Evaluate the proportion of patients achieving clinical response and biochemical response (fecal calprotectin [FC] and C-reactive protein [CRP]) at Weeks 12, 24, and 54.
- Measure improvement in patient-reported outcomes (PROs), including the urgency numeric scale (UNRS), at Weeks 12, 24, and 54.
- Assess mucosal and histological healing at Week 54 using endoscopy and biopsy.
- Evaluate changes in rectal and colonic wall thickness via ultrasound, if feasible[6].

Endpoints

Composite Endpoint:

Proportion of patients achieving deep remission at 54 ± 4 weeks, defined as: Mayo rectal bleeding subscore = 0, stool frequency subscore = 0, endoscopic subscore ≤ 1 .

Secondary Endpoints:

- Proportion of patients achieving clinical response at Weeks 12, 24, and 54, defined as
 a decrease from baseline in Mayo Clinic total score of ≥3 points and ≥30%, with a
 decrease in rectal bleeding subscore of ≥1 or an absolute rectal bleeding subscore of
 0 or 1.
- Change from baseline in PRO scores, including the urgency numeric scale (UNRS), at Weeks 12, 24, and 54.
- Proportion of patients achieving biochemical response (normalization or significant reduction in FC and CRP levels) at Weeks 12, 24, and 54.
- Safety outcomes: Incidence and severity of adverse events (AEs), serious adverse events (SAEs), and discontinuations due to AEs throughout the study.

Outcomes measurement

Primary Outcome Measures:

1. Clinical Remission at 24 and 54 ± 4 weeks

 \circ To assess the proportion of patients achieving clinical remission at 54 ± 4 weeks, defined as a modified Mayo score (MMS) with a rectal bleeding subscore of 0, stool frequency subscore of 0 or 1 with at least a 1-point reduction from baseline, and an endoscopic subscore of 0 or 1 (excluding friability).

Secondary Outcome Measures:

1. Endoscopic Remission at 54 ± 4 weeks

To determine the proportion of patients attaining endoscopic remission at 54 ± 4 weeks, defined as a Mayo endoscopic subscore of 0 or 1 (excluding friability) and UCEIS score.

2. Histologic Remission at 54 ± 4 weeks

o To evaluate histologic remission at 54 ± 4 weeks using the Nancy histological score. Remission is defined as a Nancy histological score of 0.

3. Symptomatic Remission at 12, 24 e 54 ± 4 weeks

To assess the proportion of patients achieving symptomatic remission at 12,
 24 e 54 ± 4 weeks, defined as a Mayo score with a rectal bleeding subscore of
 0 and a stool frequency subscore of 0 or 1 with at least a 1-point decrease

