• To evaluate the proportion of patients achieving disease clearance at 12, 24 e 54 \pm 4 weeks, defined as simultaneous attainment of deep remission (see above) and histologic remission (Nancy Histological Index = 0, indicating absence of significant inflammatory infiltrate)

13. Quality of Life Assessment

- To assess changes in health-related quality of life, measured using the IBD Disability Index (IBD-Disk) and the Functional Assessment of Chronic Illness Therapy–Fatigue (FACIT–Fatigue) questionnaire, 12, 24 e 54 ± 4 weeks.
- 14. Safety assessment through the 54 weeks, reporting side effects related to Etrasimod

Study Population

Inclusion Criteria:

- Adults aged ≥18 years with a confirmed diagnosis of UC for at least 6 months.
- Moderate-to-severe UC defined by a Mayo Clinic total score between 6 and 12 inclusive, with an endoscopic subscore ≥2.
- Inadequate response, loss of response, or intolerance to at least one prior biologic therapy (e.g., anti-TNF agents, vedolizumab, ustekinumab).

Exclusion Criteria:

- Diagnosis of Crohn's disease or indeterminate colitis.
- History of colectomy or anticipated need for colectomy during the study period.
- Presence of colonic dysplasia or malignancy.
- Active or latent tuberculosis not adequately treated.
- Serious uncontrolled medical conditions (e.g., severe infection, significant hepatic or renal impairment).
- Known hypersensitivity to Etrasimod or its excipients.

Intervention

Etrasimod Dosing Regimen:

- Induction Phase:
 - Etrasimod 2 mg administered orally once daily.

Maintenance Phase:

• Etrasimod 2 mg administered orally once daily up to Week 54.

Study Assessments and Visits

Baseline (Week 0):

- Comprehensive clinical assessment, including 9-point MMS.
- Endoscopic evaluation to assess mucosal appearance (endoscopic MAYO and UCEIS scores).
- Histological assessment via biopsy (Nancy score).
- Baseline PROs, including urgency numeric scale (UNRS).
- Laboratory tests: FC, CRP, complete blood count (CBC), liver and renal function tests.
- Collection of demographic and disease-specific data.
- Ultrasound evaluation of colonic and rectal wall thickness, if feasible (Milan Ultrasound Criteria).

Week 12, 24, 54 Assessments:

- Clinical response and remission assessment.
- Laboratory tests: FC, CRP.
- PRO assessments, including UNRS.
- Endoscopic and histological evaluation at Week 54.
- Safety monitoring.
- Ultrasound evaluation (Week 54, if feasible).

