Continuous data will be expressed as mean ± standard deviation (SD) or median and interquartile range (25th-75th percentile), while categorical variables will be reported as absolute and relative frequencies. Normality will be assessed using the Kolmogorov-Smirnov test and Levene's test for homogeneity of variance. The primary endpoint is the proportion of patients achieving deep remission at Week 54, defined as a binary variable. To compare paired proportions (e.g., remission status at baseline vs Week 54), McNemar's test will be used. To identify predictors of remission, multivariable logistic regression models will be applied, adjusting for baseline covariates. Repeated measures at Weeks 12, 24, and 54 will be analyzed using generalized estimating equations (GEE) with an appropriate link function (logit for binary outcomes; identity for continuous) to account for within-subject correlations over time. When evaluating continuous outcomes, repeated-measures ANOVA or linear mixed models may be used as appropriate. Between-group comparisons of continuous variables will be conducted using Student's t-test or Mann-Whitney U test, depending on data distribution. Chi-square or Fisher's exact test will be used for categorical comparisons. Associations between variables will be assessed using Spearman's correlation coefficient. Survival outcomes (if any) will be analyzed using the Kaplan-Meier method, with comparisons made using the log-rank test. Hazard ratios (HR) will also be presented using smoothed estimates to visualize changes over time. A two-tailed p-value < 0.05 will be considered statistically significant. All analyses will be conducted using SPSS v27.0, R (version 3.4.3), and EZR.

Ethical Considerations

- The study will adhere to the Declaration of Helsinki and Good Clinical Practice (GCP) guidelines.
- Written informed consent will be obtained from all participants before any studyrelated procedures.

Enrollment Period

 Duration: Enrollment is planned to commence in July 2025 or upon commercial availability of the investigational drug, which is currently accessible exclusively under compassionate use. The enrollment window will extend for 6 months from the date of drug availability. Each participant will be followed for 54 ± 4 weeks from the time of inclusion.

Recruitment Strategy:

- Patients will be recruited from multiple specialized inflammatory bowel disease (IBD) centers across different geographic regions.

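### Etrasimod is already obtainable under compassionate use, yet no eligibility criterion excludes previous or current users from this single-arm before-and-after study

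*Protocol*

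**What the plan says.** **Access before the study.** Enrollment Period sets the start at July 2025 or upon "commercial availability of the investigational drug, which is currently accessible exclusively under compassionate use". The window then runs for six months from availability.

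**Eligibility.** Study Population requires active disease: "Moderate-to-severe UC defined by a Mayo Clinic total score between 6 and 12 inclusive, with an endoscopic subscore ≥2". It also requires "Inadequate response, loss of response, or intolerance to at least one prior biologic therapy", which concerns biologics and is silent on earlier etrasimod. Of the six exclusion criteria, one names the drug: "Known hypersensitivity to Etrasimod or its excipients". None addresses previous or current use, and none sets a washout.

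**Time origin.** Enrollment Period states: "Each participant will be followed for 54 ± 4 weeks from the time of inclusion". Study Assessments and Visits labels baseline as Week 0 without placing it relative to the first dose.

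**Use of baseline.** Statistical analysis states: "The primary endpoint is the proportion of patients achieving deep remission at Week 54, defined as a binary variable". It continues: "To compare paired proportions (e.g., remission status at baseline vs Week 54), McNemar's test will be used". Several secondary outcomes (clinical response, endoscopic response, FC and CRP, urgency) are measured against baseline.

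**Safety.** The endpoint is "Incidence and severity of adverse events (AEs), serious adverse events (SAEs), and discontinuations due to AEs throughout the study".

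**The concern.** The study has one arm, so each patient's own baseline is the only comparator. Its meaning depends on that baseline being free of the study drug. The Protocol says the drug is already reachable, and the eligibility list, applied as written, does not ask whether a patient has had it.

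Two kinds of patient could enter, and they raise different problems.

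- **Current users** with a total Mayo score of 6-12 and an endoscopic subscore of at least 2. Their baseline would be on drug, and their disease has stayed active despite treatment. They have also already come through early exposure without stopping.
- **Former users** who stopped and start again. They would have an off-drug baseline and a full treatment period under observation. Their likely outcome is partly known in advance: poor if they stopped for lack of effect, better if they had responded and stopped for another reason.

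At stake are the remission rate, the changes from baseline and, for current users only, the early safety experience. The comparison by treatment line (secondary outcome 8) is also affected, because it does not say how an earlier course of etrasimod counts.

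**Working it through.** **1. What the written criteria admit**

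| Criterion | Current user, active disease | Former user, relapsed |
|---|---|---|
| Mayo 6-12, endoscopic subscore ≥2 | met | met |
| Failure of or intolerance to ≥1 biologic | can be met | can be met |
| Known hypersensitivity to the drug | not excluded if tolerated | not excluded if tolerated |
| Previous or current etrasimod | no rule | no rule |

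The activity criterion does keep out patients in remission on the drug. The current users who remain are therefore non-responders or partial responders.

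**2. What other sections imply about the start of treatment**

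- Study Design, Timeline: the treatment period has the same length as follow-up, 54 ± 4 weeks, for each participant.
- Outcomes measurement, secondary outcome 10: the 12-, 24- and 54-week time points are counted as weeks on etrasimod.
- Intervention: an induction phase comes before maintenance to Week 54.
- Sample Size Determination: the paired comparison is described as before versus after the intervention.

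All four describe treatment that starts at Week 0. Enrollment Period counts follow-up from inclusion instead. The two agree for a new starter and conflict for a current user.

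**3. The plan's own figure**

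The 68 pairs serve here only as the cohort size. Miettinen's formula with the stated inputs (ψ = 0.35 + 0.10 = 0.45, d = 0.35 − 0.10 = 0.25, two-sided α = 0.05, power 0.80) is

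n = (1.96ψ + 0.842√(ψ² − d²(3+ψ)/4))² / (ψd²) = 51.7, so 52 pairs, and 52/0.95 = 54.7, so 55 with drop-out.

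This does not reproduce 68. That is a separate matter and does not bear on eligibility.

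**4. Illustration of size: remission**

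Assumptions, not in the documents: a share f of entrants is pre-exposed and remits at rate r; new starters remit at 35%. The 35% is borrowed from the 0-1 discordant probability, read as no remission at baseline and remission at Week 54. Entry requires an endoscopic subscore of at least 2, so nobody is in deep remission at baseline, and on that reading the 0-1 proportion is the Week 54 remission rate.

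Pooled rate = (1 − f) × 0.35 + f × r, a shift of f × (r − 0.35).

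- f = 5% (0.05 × 68 = 3.4, about 3 patients), r = 0: 0.95 × 0.35 = 0.333
- f = 15% (0.15 × 68 = 10.2, about 10 patients), r = 0: 0.85 × 0.35 = 0.298

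The shift is downward when r is below 35% and upward when r is above it, as it could be in restarted former responders.

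For scale, the standard error of a 35% rate in 68 patients is √(0.35 × 0.65 / 68) = 0.058, so the 95% half-width is 1.96 × 0.058 = 0.113, about 11 points.

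**5. Illustration of size: power**

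The plan's inputs with 64 evaluable pairs (68 × 0.95 = 64.6) give

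Φ[(d√(nψ) − 1.96ψ) / √(ψ² − d²(3+ψ)/4)] = 0.88.

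With f = 10% and r between 0 and 0.10, the 0-1 probability becomes 0.9 × 0.35 + 0.1 × r = 0.315 to 0.325. Holding the 1-0 probability at 0.10, power is 0.79 to 0.82.

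**6. Illustration of size: safety, current users only**

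If new starters stopped for adverse events at an assumed 10% and current users had no such stops, the pooled rate would be (1 − f) × 10%: 9.5% at f = 5% and 8.5% at f = 15%.

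**The case against.** The strongest reply is that the Protocol already describes a study in which etrasimod starts at Week 0, as the four places in step 2 show. A reader who takes the follow-up sentence in Enrollment Period alone might infer that Week 0 is generally not pre-treatment and that Week 54 falls at an unknown time on drug. The documents do not support that. It would be true only of a current user, and such a patient does not fit the rest of the design. This part of the objection stands. It does not close the gap, because a dosing heading or a timeline entry is not an eligibility rule, and centres could apply it differently.

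A reader might also infer that every pre-exposed patient removes early exposure from the safety data. That is wrong for former users, who are re-exposed under observation from Week 0.

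Third, the documents do not say that the participating centres treated anyone under compassionate use, or how many. That some did is plausible for specialised IBD centres, but it is an assumption.

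Fourth, the illustrated shift of 2 to 5 points is under one standard error. It assumes no remission in any pre-exposed patient and leaves out the upward effect of restarted responders. At a 10% share, power stays near the planned 0.80. This stands as a limit on size. It does not make the shift harmless: a selection effect is a bias, which a larger sample does not average out.

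**Conclusion.** The gap is real and belongs in the Protocol, because it concerns who may enter. The Protocol states that the drug is obtainable before enrolment, and its eligibility list would admit previous and current users. Current users would contradict the implied start of treatment at Week 0, and nothing excludes them.

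The probable direction is downward for remission, because the activity criterion selects current users with persisting disease. It is not certain, because restarted former responders could push the rate up. For early adverse events and discontinuations the tendency is towards understatement, through current users only.

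It would go too far to say that the rates are distorted or that the safety rates are too low. The documents give no count of pre-exposed patients, and the fall from 35% to about 33-30% rests wholly on an assumed 5-15% share with no remission. This is an inexpensive improvement that should be made. It does not show that the results will be materially wrong.

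**What to change.** 1. Add one exclusion criterion: any previous or current exposure to etrasimod, including compassionate use. If the centres wish to keep such patients because of the study's real-world aim, record prior exposure (dates, response, reason for stopping) at baseline and report them as a separate cohort, outside the primary remission rate and the main safety rates. The baseline list does not name prior etrasimod, although its general entry for disease-specific data could hold it.
2. Reconcile the follow-up sentence in Enrollment Period with the start of treatment implied elsewhere, by stating that Week 0 assessments precede the first dose of etrasimod.

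The cost is one eligibility line and one definition. A few potential participants are lost, which may slow recruitment slightly within the six-month window. The separate-cohort option avoids turning those patients away but adds baseline items, and they would not count towards the 68.
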